2.4 Participant Information and Informed Consent (HRO Art. 8, Annex 2/1.3-1.5)

The investigators or study nurses of each participating site will explain to each participant the nature of the study, its purpose, the procedures involved, the expected duration, the potential risks and benefits and any discomfort it may entail. Each participant will be informed that the participation in the study is voluntary and that he/she may withdraw from the study at any time and that withdrawal of consent will not affect his/her subsequent medical assistance and treatment.

The participant must be informed that his/her medical records may be examined by authorised individuals other than their treating physician.

All participants for the study will be provided a participant information sheet and a consent form describing the study and providing sufficient information for the participant to make an informed decision about their participation in the study. Enough time (a minimum of 24hours) needs to be given to the participant to decide whether to participate or not.

The patient information sheet and the consent form will be submitted to the CEC and to the competent authority (as applicable) to be reviewed and approved. The formal consent of a participant, using the approved consent form, must be obtained before the participant is submitted to any study procedure.

The participant should read and consider the statement before signing and dating the informed consent form, and should be given a copy of the signed document. The consent form must also be signed and dated by the investigator (or his designee) and it will be retained as part of the study records.

See also Chapter 3.3 Risk-benefit assessment.

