For the analysis of all-cause and pneumonia-related mortality flexible parametric survival models will be applied that allow for a flexible approach in modelling and estimation of the baseline hazard of death (27, 28). Survival time will start at the date of initiation of first rehabilitation and censoring is at date of discharge from local first rehabilitation or at date of death. The analysis of pneumonia-related mortality will be adjusted for competing risks, i.e., events that either hinder the observation of the event of interest or modifies the chance that this event occurs. Potential competing risks for the event of pneumonia-related mortality during first SCI rehabilitation for instance include other causes of mortality (e.g., septicaemia, neoplasm) or transfer to another rehabilitation clinic or another facility to receive specialized treatment. In such cases the censored time-to-events reflect a form of incomplete data that may induce bias in estimates of pneumonia risk from unadjusted analyses. Competing risk analysis accounts for competing events as to provide an unbiased estimate of the pneumonia-related hazard of death during first rehabilitation (29, 30).

Predictors; extraneous, mediating, moderating and confounding variables

The main predictors (exposures of interest) in the modelling of the primary outcome and secondary outcomes include the degree of motor and sensory neurological impairment as captured by the ASIA Impairment Scale (35); lesion level classified as paraplegia or tetraplegia; PCF and partial dependency on mechanical ventilation (a minimum of 1hour free of ventilator dependency during the day). Further predictors for secondary outcomes include an index of physical activity as well as an indicator for respiratory training, assessed using a questionnaire.

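### The mortality clock starts at the beginning of rehabilitation, but patients enter the data only at consent, and no delayed entry is planned

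*Combined protocol and SAP*

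**What the plan says.** Section 8.3.2 (Advanced regression modelling, secondary outcomes) sets the follow-up rule for all-cause and pneumonia-related mortality. The origin is given as: "Survival time will start at the date of initiation of first rehabilitation". The end is given as: "censoring is at date of discharge from local first rehabilitation or at date of death". The models are flexible parametric survival models, chosen because they "allow for a flexible approach in modelling and estimation of the baseline hazard of death".

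Enrolment is described elsewhere:

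- Section 6.1 admits patients in initial rehabilitation.
- Section 2.4 says: "Enough time (a minimum of 24hours) needs to be given to the participant to decide whether to participate or not". It adds that consent "must be obtained before the participant is submitted to any study procedure".
- The assessment table in section 7 places screening and consent before T1, and T1 at 28±12 days after injury.

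No section mentions delayed entry, left truncation, or a risk set that opens at consent.

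**The concern.** A patient who dies or leaves between the start of rehabilitation and consent never appears in the data set. Every enrolled patient has therefore survived to consent. If consent comes after rehabilitation starts, the interval between them is event-free by design, and the stated origin still counts it as time at risk. The denominator is inflated and the numerator is not, so the bias runs one way, towards too low a death rate. More patients do not reduce it, and the confidence interval does not reflect it.

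The distortion is concentrated in the earliest period, where it alters the baseline hazard that the flexible models are meant to describe. Mortality due to pneumonia is a named secondary endpoint (section 4.2) and the subject of one of the three planned papers (section 10.1).

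The existing safeguards do not reach this. The participation weighting in section 8.3.2 compares invited patients with participants, so it cannot recover deaths before invitation, and it sets no entry time. Time since injury is listed only as a covariate. Imputation fills in missing values for enrolled patients but does not restore patients who were never enrolled.

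**Working it through.** The plan gives no mortality rate, number of deaths, length of stay or interval from rehabilitation start to consent, so there is no mortality figure to reproduce. From the documents come the time origin, the consent requirement, the 24-hour minimum for the decision and the planned 625 patients. The lag L, the mean follow-up after entry M and the daily death hazard h are assumptions.

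**Overall rate.** With constant hazard h, n patients yield about n·h·M deaths after entry. The correct rate is deaths/(n·M). The stated rule gives deaths/(n·(M+L)). The relative understatement is L/(M+L):

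| Lag L | M = 90 d | M = 150 d | M = 180 d |
|---|---|---|---|
| 1 d | 1/91 = 1.1% | 1/151 = 0.7% | 1/181 = 0.6% |
| 7 d | 7/97 = 7.2% | 7/157 = 4.5% | 7/187 = 3.7% |
| 14 d | 14/104 = 13.5% | 14/164 = 8.5% | 14/194 = 7.2% |

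**Early hazard.** Over the first 30 days of rehabilitation (a window chosen for illustration), with exponential exit after entry, the time truly at risk is A = M·(1 − exp(−(30−L)/M)) and the time counted is A + L. For L = 7, A/(A+L) is 0.744 (M = 90) to 0.755 (M = 180), so the hazard is understated by about 25%. If lags are spread uniformly over 1 to 14 days the ratio is 0.726 to 0.738, about 26-27%. For L = 1 it is 0.961 to 0.964, about 4%.

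**Check by simulation.** Two million patients per setting, uniform lag, true 150-day mortality 4.0%. With a mean lag of 7 or 14 days, ignoring entry time gives 3.80% or 3.65% under a constant hazard, and 3.39% or 3.10% if the hazard falls over time (Weibull shape 0.6). Using the entry time gives 3.97% to 4.01% in these four settings. A falling hazard therefore makes the understatement larger than in the table.

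**Sampling error for comparison.** Expected deaths are 625·h/(h + 1/M). For h = 0.00005 to 0.0003 per day and M = 150 this is 4.7 to 26.9 deaths. Over M = 90 to 180 it is 2.8 to 32.0. The relative 95% margin is about 1.96/√deaths: ±91% to ±38% for M = 150, and ±117% to ±35% over the whole range. All entries in the table are smaller. About 0.5 to 5 deaths would fall in the first 30 days, with a margin of at least 1.96/√4.9 = ±88%.

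**Hazard ratios.** If L and M are the same in two groups, both rates are multiplied by M/(M+L) and their ratio is unchanged. If L were 14 days in one group and 1 day in the other with M = 150, the crude rate ratio would be multiplied by 151/164 = 0.92. The documents show no such difference.

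**The case against.** The strongest reply is that the lag is unknown. The 24 hours are time to decide, counted from when the patient is informed and not from the start of rehabilitation, and a patient who consents by that start has no lag. The only documented interval gives an effect of about 1% or less. The planned paper concerns factors associated with mortality, so hazard ratios matter more than the baseline. Deaths will be few. All of this stands and limits the size. It does not make the rule correct, because the origin is stated and no entry time is.

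A reader might infer that models using T1 measurements carry event-free time all the way to T1, because the main predictors include "PCF and partial dependency on mechanical ventilation" and peak cough flow is first measured at T1. The documents do not support this for the main analysis. The section headed Datasets to be analysed commits to multiple imputation, and the section headed Ancillary analysis calls the imputed results the main analysis. A consented patient who dies before T1 need not leave the model. Entry at T1 would also be costly: for a 14-day gap between consent and T1, 1 − exp(−(h + 1/M)·14) gives 7.5-14.8% of deaths discarded, about the size of the bias from a 14-day lag (7.2-13.5%).

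A reader might also see a contradiction in censoring at discharge while listing "transfer to another rehabilitation clinic or another facility to receive specialized treatment" as a potential competing risk. That is an undefined rule, not an established contradiction. The censoring sentence covers both mortality outcomes and the competing-risk text only pneumonia-related death. That a transfer counts as a discharge is an inference. Censoring a transfer is valid for a cause-specific hazard. The statement "Competing risk analysis accounts for competing events as to provide an unbiased estimate of the pneumonia-related hazard of death during first rehabilitation" would be in question only if a subdistribution hazard or cumulative incidence were meant, and the text does not name the target.

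**Conclusion.** The point holds for the interval from rehabilitation start to consent. For patients who consent after rehabilitation starts, the stated origin counts event-free time as at risk, and the death rate and early hazard are understated. With a constant hazard and mean follow-up of 90 to 180 days after entry, the overall rate is low by 0.6-1.1%, 3.7-7.2% or 7.2-13.5% for lags of 1, 7 or 14 days. It would be more if the hazard falls over time, and nothing if consent is always in place by rehabilitation start. The lags, stays and hazards are assumptions.

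A reader might go further and conclude that the mortality results would be unusable or that the predictor effects are biased. The documents do not support that: the bias is below sampling error, and hazard ratios move mainly if the lag differs between groups, which nothing in the plan shows. The primary ROC analysis and the sample size of 625 are untouched. The case for changing the plan is that the bias is systematic and its correction costs almost nothing.

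**What to change.** Keep the time origin. State that each patient enters the risk set at the later of rehabilitation start and consent date, in both the all-cause and the pneumonia-related mortality models. Define the date of rehabilitation start and report the distribution of the lag to consent. Keep consented patients who die before T1 in the main analysis through the planned imputation. Use entry at T1 only in the complete-case comparison of models with T1 covariates such as peak cough flow.

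The cost is a few sentences, one entry-time option in the software, and the dates of rehabilitation start, consent, T1, departure and death. Person-time is slightly reduced. Left truncation assumes that, given the covariates, the timing of consent is unrelated to the risk of death; the lag distribution helps to judge this.

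Two minor wording changes can go in at the same time. First, say that death is the event, and that live discharge or transfer ends follow-up. Second, name the target for pneumonia-related mortality. With a cause-specific hazard, transfer may be censored. With a subdistribution hazard or cumulative incidence, code transfer and live discharge as competing events alongside death from other causes.

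### Live discharge is coded as censoring in the mortality analysis while transfer counts as a competing event, so any absolute or subdistribution-based risk of death in rehabilitation taken from the models would be wrong

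*Combined protocol and SAP*

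**What the plan says.** All of the following comes from the mortality paragraph of Section 8.3.2 (Advanced regression modelling), unless another section is named.

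- Model for both mortality outcomes (all-cause and pneumonia-related): "flexible parametric survival models will be applied that allow for a flexible approach in modelling and estimation of the baseline hazard of death".
- Time origin: "Survival time will start at the date of initiation of first rehabilitation".
- End of follow-up, under one rule that serves both outcomes: "censoring is at date of discharge from local first rehabilitation or at date of death".
- Competing risks: "The analysis of pneumonia-related mortality will be adjusted for competing risks". No such step is stated for all-cause mortality.
- Definition of a competing risk: "events that either hinder the observation of the event of interest or modifies the chance that this event occurs".
- Examples, given as an open list: "other causes of mortality (e.g., septicaemia, neoplasm) or transfer to another rehabilitation clinic or another facility to receive specialized treatment". Ordinary live discharge is not among them.
- Reason given for the adjustment: "the censored time-to-events reflect a form of incomplete data that may induce bias in estimates of pneumonia risk" when the analysis is unadjusted.
- Stated result: an "unbiased estimate of the pneumonia-related hazard of death during first rehabilitation". The supporting citations include the subdistribution-hazard regression model (reference 30).

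The visit table in Section 7 ties the last visit to discharge and schedules none afterwards. Section 4.2 lists pneumonia mortality as a secondary endpoint, and Section 10.1 plans a separate paper on it and its associated factors.

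**The concern.** Transfer and ordinary discharge both end observation with the patient alive. The plan calls the first a competing event and the second censoring. By its own definition, discharge qualifies as competing, and its own warning about bias from censored times applies to discharge too. The word 'local' adds to the muddle: a patient transferred elsewhere has also left local first rehabilitation and so falls under both rules.

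The coding matters because different quantities need different handling of discharge. A cause-specific hazard among current inpatients can be estimated with discharge censored. The probability of dying during rehabilitation cannot. Censoring discharged patients produces the mortality that would be seen if nobody left and everyone kept the inpatient hazard. A subdistribution model that censors discharge inherits the same problem in its coefficients: groups with longer stays really do have more deaths during rehabilitation at the same daily hazard, and that coding hides it.

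**Working it through.** The documents contain no mortality rate, expected number of deaths, length of stay or power statement for mortality, so there is no figure of the plan's own to reproduce. Every death rate and stay below is an assumption.

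**1. Constant hazard, exponential stay.** Let h be the daily death hazard and D = 1/(mean stay) the daily rate of live discharge.

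- Risk of dying in rehabilitation by day t (discharge competing): CIF(t) = h/(h+D) × (1 − exp(−(h+D)t)).
- One minus survival (discharge censored): 1 − S(t) = 1 − exp(−ht).

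With h = 0.0001 and t = 365, 1 − S = 1 − exp(−0.0365) = 3.58% for any stay.

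| Mean stay (days) | CIF(365) | (1 − S)/CIF, day 365 | (1 − S)/CIF, day 180 |
|---|---|---|---|
| 100 | 0.0001/0.0101 × (1 − exp(−3.69)) = 0.97% | 3.7 | 2.2 |
| 150 | 0.0001/0.00677 × (1 − exp(−2.47)) = 1.35% | 2.65 | 1.7 |
| 200 | 0.0001/0.0051 × (1 − exp(−1.86)) = 1.66% | 2.2 | 1.5 |

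Doubling h to 0.0002 leaves the day-365 ratios almost unchanged (3.7, 2.6, 2.2). Stay length and hazard shape drive the size, not the death rate.

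**2. Wider range of shapes.** The hazard was set so that 2% truly die in rehabilitation. Stays were gamma-distributed with mean 120, 180 or 240 days and coefficient of variation 0.4, 0.6 or 1.0. The death hazard was either constant or declining as exp(−t/60 days).

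| Scenario | Day 180: 1 − S vs CIF (ratio) | Day 365: 1 − S vs CIF (ratio) |
|---|---|---|
| Mean 180, CV 0.6, constant | 2.01% vs 1.54% (1.30) | 4.03% vs 1.94% (2.07) |
| Mean 180, CV 0.6, declining | 2.18% vs 1.97% (1.11) | 2.29% vs 2.00% (1.15) |
| Highest: mean 120, CV 1.0, constant | 3.01% vs 1.57% (1.92) | 6.02% vs 1.91% (3.15) |
| Lowest: mean 240, CV 0.4, declining | 1.99% vs 1.95% (1.02) | 2.09% vs 2.00% (1.04) |

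In the 180-day, CV 0.6 case the ratios barely change when 1% or 5% die. The excess is positive in every scenario.

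**3. Hazards with discharge censored.** In a simulation of 2,000,000 patients with discharge unrelated to prognosis, true rates of 1.00 and 2.00 per 10,000 patient-days were estimated as 1.00 and 2.02. The true hazard ratio of 2.0 was estimated as 2.02 with equal stays and 1.97 when exposed patients stayed longer. Censoring at discharge did not bias the hazards. Between 97% and 98% of simulated patients left alive.

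**4. Effect estimates on the subdistribution scale.** In the same simulation with longer stays in the exposed, the ratio of cumulative incidences was 3.08 against a hazard ratio of about 2. For the simplest case, use step 1 with equal death hazards and mean stays of 200 against 100 days. With discharge competing, the ratio of log(1 − CIF) at one year is log(1 − 0.01656)/log(1 − 0.00965) = 1.72. With discharge censored it is 1.0. In a subdistribution model, the coding of discharge therefore changes the coefficients as well as the absolute risk.

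**The case against.** The strongest reply is that the plan's named target is a hazard. It names no survival curve, no one-minus-survival estimate, no cumulative mortality and no time horizon, and censoring at discharge is standard for a cause-specific hazard. This stands, and step 3 supports it. A reader might infer that the planned mortality results are overstated in general. The documents do not support that: it is true of absolute risks taken from the model, which the plan does not promise, and not of the hazards that it does.

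Second, Section 8.3.1 (Descriptive analysis) presents secondary outcomes as frequencies with binomial intervals. Leaving aside dropout and transfer, deaths divided by patients is the in-rehabilitation proportion, with live discharge correctly counted as no death. This also stands, so a sound crude figure would exist overall and by pneumonia status. It does not settle how discharge is coded in the competing-risk regression.

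Third, the end-of-follow-up sentence also lists death, which is the event for all-cause mortality, so 'censoring' there may simply mean end of observation. The list of competing events is open and the definition is broad enough to include discharge. That is a fair reading, but the only explicit rule about discharge makes it censoring, and two analysts could code it differently.

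Fourth, ratios of two or more at one year come from the constant-hazard scenarios, at a horizon the plan never sets; declining-hazard scenarios are much milder. This is right, and is why the full range is shown.

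A reader might also infer that discharge is informative because patients leave once they have recovered. The documents do not say why patients are discharged, and none of the calculations rests on it. If true, it would be a separate problem, and one that would affect the hazards too.

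**Conclusion.** The point holds in a limited form. The coding of live discharge is inconsistent with the plan's own definition of a competing risk, and all-cause death has no competing-event handling. Cause-specific hazards and hazard ratios are unaffected provided discharge is non-informative given the covariates. What would go wrong is any absolute risk of death in rehabilitation that still censors discharge (one minus survival, or a cumulative incidence), and any subdistribution-hazard coefficient, which the citation of reference 30 leaves open.

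The direction for absolute risk is upward. The size is uncertain: about 1.02 to 1.9-fold at day 180 and 1.04 to 3.2-fold at day 365 across the gamma-stay scenarios with 2% dying, and up to 3.7-fold at one year with a constant hazard and a 100-day mean exponential stay. That last case gives about 2.2-fold at day 180.

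This is a secondary endpoint with few expected deaths: 2% of 625 is 12.5, and the risks in step 1 give about 6 to 10. It should still be corrected before analysis, because a written coding rule conflicts with the competing-risk analysis promised in the same paragraph.

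**What to change.** In the mortality paragraph of Section 8.3.2 (Advanced regression modelling):

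1. State the mortality estimands: the cause-specific hazard, the cumulative incidence of death during rehabilitation, or both.
2. For factors associated with death, report cause-specific hazard ratios with discharge censored, and state the assumption that discharge is non-informative given the covariates.
3. Whenever a cumulative incidence or subdistribution hazard is estimated, code live discharge as a competing event, for all-cause as well as pneumonia-related death.
4. Report absolute risk as cumulative incidence, by the Aalen-Johansen estimator or from the cause-specific flexible parametric models. Do not present one minus survival as in-rehabilitation mortality.
5. Correct the wording that censors at death: death is the event for all-cause mortality, and death from another cause is a competing event for pneumonia-related mortality.

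The cost is one event code, built from the discharge date that the existing rule already requires, and a few sentences of text. No new data are needed.

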Objective(s):	The main objective of this study is to evaluate 'cut-off levels' of inspiratory muscle strength as predictor for pneumonia in individuals with SCI (diagnostic accuracy). Additionally, to evaluate lifestyle and treatment parameters as well as personal- and lesion characteristics as further potential determinants of pneumonia as well as the impact of pneumonia on quality of life and mortality.
Endpoint(s):	Primary study outcome: Diagnostic accuracy of inspiratory muscle strength for prediction of pneumonia. Main secondary study outcomes: Personal- and lesion characteristics, other parameters of respiratory function, lifestyle and treatment parameters, quality of life and mortality
	due to pneumonia.

Inclusion / Exclusion	Inclusion:								
criteria:	Male and female, age ≥ 18 years, AIS A, B, C or D lesion, lesion level C1- T12								
	Exclusion:								
	Neurologic diseases (e.g. MS, ALS), 24h mechanical ventilation								
	dependency, mental disorders								
Project assessments,	Measurements:								
procedures:	- in- and expiratory muscle strength (5min)								
	- lung function (FVC, FEV ₁ , PEF, PCF) (10 min) Questionnaires:								
	- ISCoS core data-set								
	- ISCoS pulmonary function data sets								
	- ISCoS quality of life questionnaire								
	- questionnaire on individual respiratory muscle training, regular physical								
	exercise and therapies								
	- individual medication/vaccination and other medical complications will								
	be assessed from patient's medical records								
	All measurements will be performed at each measurement time-point (up								
	to 4 times during inpatient rehabilitation) and last about 40 min per patient								
	and measurement time-point in total (time with patient).								
Number of	Regarding the in- and exclusion criteria, we made a calculation of a								
Participants:	realistic numbers of subjects who can be recruited for this study per year								
	and center, based on the number of patients admitted to the								
	corresponding center during the last years								
	Estimated numbers of patients per year for each center are as follows:								
	Switzerland: SPZ Nottwil: 30 patients								
	Balgrist Zuerich: 20 patients								
	Rehab Basel: 20 patients								
	CRR Sion: 5 patients								
	Germany: BG Hamburg: 30 patients								
	Austria: Haering: 30 patients								
	Tobelbad: 30 patients								
	Australia: Heidelberg: 40 patients								

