4. OBJECTIVES, ENPOINTS/OUTCOMES AND OTHER STUDY VARIABLES

4.1 Objectives (STROBE 3)

The primary objective of the study is to evaluate diagnostic accuracy of 'cut-off levels' for inspiratory muscle strength as predictor for pneumonia in individuals with SCI.

Specific aims include:

1) to evaluate lifestyle and treatment parameters as well as personal- and lesion characteristics as potential other determinants for pneumonia;

2) to evaluate the association between pneumonia and quality of life as well as mortality due to pneumonia.

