7.3 Assessment of secondary endpoint/outcome(s)

Secondary endpoints of this study include the various lung parameters mentioned above; other medical complications; quality of life; co-morbidities, medication and vaccination and mortality, in particular pneumonia-related death.

The various lung parameters thus include maximal inspiratory pressure (MIP), maximum expiratory pressure (MEP), vital capacity (FVC), forced expiratory volume in 1 second (FEV₁), and peak expiratory flow (PEF).

The peak cough flow (PCF) will be measured by having the person cough as forcefully as possible through a peak flow meter.

Medical complications will be assessed from the patient's medical records by the study nurse without involvement of the patient.

Quality of life (QoL) will be evaluated using the Quality of Life Basic Data Set of the International Spinal Cord Injury Datasets. This measurement instrument accepts (QoL) as a multi-facetted concept and includes three questions as to capture general quality of life (overall well-being), rating of physical health, and satisfaction with psychological health (17).

Co-morbidities will be assessed only once using the ICD-10 codes after the end of inpatient rehabilitation. This will also be assessed from the patient's medical records by the study nurse without involvement of the patient.

Medication and vaccination will be assessed at each measurement time-point (T1-T4) from the patient's medical records by the study nurse without involvement of the patient.

Mortality will be defined as pneumonia-related, if a prevailing event of pneumonia was clinically resolved as the initiating factor of the cascade of morbid events leading directly to death. Similarly, other causes of death will be recorded as part of all-cause mortality and as potentially competing risks of death.

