8.3.1 Descriptive analysis

Descriptive statistics involving demographic data, lesion characteristics, life style characteristics, medication and vaccination, partly mechanical ventilation dependency, smoking, respiratory muscle

training and physical exercise as well as primary and secondary outcome parameters will be presented as mean (standard deviation) and median (25% and 75% quartile) or frequency (binomial 95% confidence interval), where appropriate. Descriptive statistics will be provided for the overall sample as well as stratified for the two groups that are discriminated by the event of at least one event of pneumonia during the study period.

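### No named analysis estimates the synopsis objective on pneumonia and mortality, and the one stated with/without-pneumonia comparison is biased towards no harm

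*Combined protocol and SAP*

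**What the plan says.** **Objective.** The synopsis (Objective(s)) includes "the impact of pneumonia on quality of life and mortality", with pneumonia as the exposure and death as an outcome. Its background adds that such relationships are still assumptions that need a large prospective cohort. Section 4.1 words the aim as "to evaluate the association between pneumonia and quality of life as well as mortality due to pneumonia". The synopsis endpoint line, the endpoint list in 4.2 and the planned paper in 10.1 also speak of deaths caused by pneumonia.

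**Endpoint.** Section 7.3: "Mortality will be defined as pneumonia-related, if a prevailing event of pneumonia was clinically resolved as the initiating factor" of the events leading to death.

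**Models.** Section 8.3.2 (Advanced regression modelling): "For the analysis of all-cause and pneumonia-related mortality flexible parametric survival models will be applied", from the start of first rehabilitation to discharge or death, with competing risks handled for pneumonia-related death. The sentence that opens "The main predictors (exposures of interest) in the modelling of the primary outcome and secondary outcomes include" goes on to AIS grade, para-/tetraplegia, peak cough flow and partial ventilator dependency. Then: "Further predictors for secondary outcomes include an index of physical activity as well as an indicator for respiratory training". The covariate paragraph adds gender, age, time since injury, smoking, medication, vaccination and local influenza activity. Pneumonia is in none of these lists, and no time-dependent, landmark or multistate method is mentioned.

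**Comparison by pneumonia.** Section 8.3.1 (Descriptive analysis) presents primary and secondary outcomes, mortality among them, overall and "stratified for the two groups that are discriminated by the event of at least one event of pneumonia during the study period".

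**The concern.** If the synopsis objective is meant, the plan names no analysis that answers it. A death can be pneumonia-related only in a patient who had pneumonia, so that endpoint has no comparison group. Only all-cause death can carry the contrast, and pneumonia is not assigned to that model.

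What remains is the ever/never split. It classifies patients by something that happens during follow-up. A patient enters the pneumonia group only by staying alive and in rehabilitation until the event, so all time before the event is free of death by construction. A patient who dies early, before any pneumonia, falls in the never group. This immortal time lowers apparent mortality in the pneumonia group. A reader of the mortality results could conclude that pneumonia does no harm, or even protects, when the grouping alone produced the pattern.

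**Working it through.** **1. The plan's own figures (8.1, 3.1).** 250 patients per year × 2.5 years = 625. Incidence 0.80 × 0.51 = 0.408, rounded to 40%. 625 × 0.40 = 250 cases. These reproduce. The sizing concerns the AUC; no expected deaths, death rate, length of stay or power for mortality is given. Everything below on those quantities is an assumption.

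**2. Size of the bias, by hand.** Assume a fixed stay L, rare deaths at a constant hazard unrelated to pneumonia (true hazard ratio 1), and 40% with pneumonia.

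- Constant pneumonia hazard: the cumulative hazard is a = −ln(0.6) = 0.511. The share of all person-time that follows pneumonia is f = 1 − 0.4/0.511 = 0.217. Deaths in the ever group can occur only in that share. Ratio of proportions dead = (0.217/0.4) / (0.783/0.6) = 0.542/1.305 = 0.42.
- Front-loaded hazard (Weibull shape 0.5): f = 1 − 2[1 − (1 + a)e^(−a)]/a² = 1 − 2(1 − 1.511 × 0.6)/0.261 = 0.283. Ratio = (0.283/0.4) / (0.717/0.6) = 0.708/1.194 = 0.59.

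The correct answer is 1 in both cases.

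**3. Simulation over other stays.** Mean stay 180 days (fixed, gamma or exponential), 3% or 10% dying, about 40% with pneumonia. A separate run used a lognormal stay with median 100 days and 1 to 5% dying. With a true hazard ratio of 1:

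| Stay | Proportions dead, constant / front-loaded | Death-rate ratio, constant / front-loaded |
|---|---|---|
| Fixed or gamma | 0.43–0.57 / 0.59–0.70 | 0.41–0.42 / 0.59–0.60 |
| Lognormal | 0.55 / 0.69 | 0.40 / 0.59 |
| Exponential | 1.00 / 0.99–1.00 | 0.38 / 0.56–0.57 |

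With exponential stays, death and discharge compete at constant hazards, so the proportion dead is the same in both groups. The rate ratio, with person-time counted from the start of rehabilitation, stays biased.

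**4. When pneumonia is truly harmful** (fixed, gamma and exponential stays).

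- Hazard ratio 2: rate ratio 0.74–1.19, ratio of proportions 0.83–1.97.
- Hazard ratio 3: rate ratio 1.09–1.77, ratio of proportions 1.23–2.93.
- The rate ratio passes 1 at a true hazard ratio of about 1.7 (front-loaded) to 2.7 (constant hazard, exponential stay).

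**5. Pneumonia counted from its event date.** The rate ratio is 0.99–1.01 at a true value of 1 (0.97–1.01 in the lognormal run), 1.98–2.04 at 2 and 2.98–3.04 at 3.

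**6. Precision available.** Deaths needed for 80% power, two-sided 5%: d = (1.960 + 0.842)² / [p(1 − p)(ln HR)²] = 7.849 / [p(1 − p)(ln HR)²].

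- With p = 0.40: 199 deaths for HR 1.5, 69 for HR 2 and 28 for HR 3, that is 32%, 11% and 4.5% of 625.
- With p = 0.217 (step 2): 97 for HR 2 and 39 for HR 3.
- Detectable HR = exp√[7.849 / (0.24 d)]: at 1% deaths (d = 6.25) 9.9; 2% 5.0; 3% 3.7; 5% 2.8; 10% 2.1. Less exposed time makes these larger.
- Pneumonia-related deaths among 250 cases, at an assumed case fatality of 1%, 2%, 5% or 10%: about 3, 5, 13 or 25.

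**The case against.** The strongest reply is that the objective is narrower than the synopsis line suggests. Section 4.1, the endpoint lists and the publication plan all concern deaths caused by pneumonia and their correlates, and the competing-risk model in 8.3.2 analyses exactly that. This stands in part. It would be wrong to infer that the planned mortality paper has no analysis behind it. It does not remove the synopsis objective, so the sections have to be reconciled.

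Second, a reader might infer that pneumonia is excluded from every mortality model. The documents do not say so: the predictor lists are worded as open, and the modelling strategy is to be settled with DAGitty. The accurate statement is that pneumonia is not named. For a stated objective that is still a gap, because the exposure and its timing are left to a later choice.

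Third, a reader might infer that the plan will make pneumonia look protective. The split is descriptive and would give proportions with binomial intervals, not death rates. The proportions are nearly unbiased under exponential stays, and a large true harm still shows (step 4). Only the direction of the bias is supportable, and its size depends on assumptions.

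Fourth, the listed covariates invite a charge of overfitting. No section specifies a model containing all of them, and the number of deaths is unknown, so that charge is not made here.

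**Conclusion.** The point holds in a limited form. The synopsis sets an objective for which no named analysis gives an estimate, other sections word the aim more narrowly, and the only stated comparison of mortality with and without pneumonia carries immortal-time bias.

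Under no true effect, the ratio of proportions dead is about 0.43 to 0.70 for fixed, gamma or lognormal stays and about 1 for exponential stays; the death-rate ratio is about 0.4 to 0.6. On the rate scale a true hazard ratio of up to about 1.7 to 2.7 could be hidden; larger harm would appear, though understated. These figures rest on the plan's 40% incidence and on assumed stays, death rates and timing of pneumonia. The absence of pneumonia from the named predictors, and the lack of a comparison group for pneumonia-related death, need no assumptions. A secondary aim is affected, not the primary analysis of diagnostic accuracy.

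**What to change.** - **Objectives:** reconcile the synopsis with 4.1, 4.2 and 10.1, and state whether the target is the effect of pneumonia on all-cause death, the burden of pneumonia-related death, or both.
- **8.3.2, for the synopsis objective:** model all-cause death with pneumonia as a time-dependent exposure that switches on at its recorded event date. Use a small adjustment set taken from the causal diagram, including partial ventilation if the diagram requires it, and a penalised fit if deaths are few. State the expected number of deaths.
- **8.3.1 (Descriptive analysis):** omit mortality by ever/never pneumonia, or label it as not interpretable as an effect of pneumonia.
- **Pneumonia-related death:** report case fatality and cumulative incidence with 95% confidence intervals, and keep any regression to a number of parameters that the observed deaths support.

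The cost is plan wording. Section 7.2 already records the date of each pneumonia, and 8.3.2 already uses dates of death and discharge. The drawback is precision: at assumed death rates of 1 to 3%, only hazard ratios of about 4 to 10 are detectable with 40% exposed, so the mortality results would make a narrower claim with wide intervals.
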